## Revision History:

Version Number	Version Date	Summary of Revisions Made:
1	March 23, 2016	[REDACTED]
2	July 21, 2016	[REDACTED] [REDACTED] [REDACTED] [REDACTED] [REDACTED] [REDACTED]

## 1 INTRODUCTION

This document is a protocol for a clinical research study sponsored by Masimo Corporation. The study will be conducted in compliance with stipulations of this protocol, the conditions of IRB approval, ISO-14155 and International Conference on Harmonization Good Clinical Practice guidelines ICH GCP.

### 1.1 Background and Rationale

The accurate measurement of circulating blood hemoglobin (Hgb) levels is one of the cornerstones of optimal treatment for traumatic injury and severe hemorrhage, the leading cause of death in people 1 to 40 years of age. In an autopsy study from the conflicts in Iraq and Afghanistan, fully 86% of all potentially preventable deaths were from truncal hemorrhage [Kelly 2008]. Likewise, in the civilian arena, the leading cause of potentially preventable death is early truncal hemorrhage [Demetriades 2004], with most deaths occurring within 6-12 hours of admission [Holcomb 2008, Clarke 2002, Moore 2008]. Measurement of Hgb requires blood to be drawn and subjected to laboratory analysis, resulting in delays of up to one hour before data are returned. This time lag can be critical in patients who have internal bleeding, a situation which can be difficult to detect even for an experienced clinician. Despite conventional teaching, the Hgb levels do change rapidly, and the first Hgb on admission to the hospital is highly predictive for blood loss. Thus, a portable, accurate, rapid, noninvasive measurement system is needed to improve quality and efficiency of treatment. In 2012, a study was conducted at Memorial Hermann Hospital (MHH) to evaluate Masimo's Radical-7, a non-invasive pulse co-oximeter, for Code 3 (highest acuity status) trauma patient during the first twenty four hours following patient presentation to the Emergency Department. One parameter measured by the device was the non-invasive Hgb (SpHb) and was compared to any laboratory Hgb (tHb) that was available for clinical care. The results of the study were recently published and it was found that while SpHb technology showed promise, it still required further refinement in order to be used for management of severely injured trauma patients [Moore 2013]. Since the conclusion of that study, the technology has continued to improve and the latest SpHb sensor revision has been designed to provide more accurate values in cases of varying oxygen saturation and in cases of large fluctuations in peripheral perfusion; the latter is often a compensatory or medically- induced physiological response which is often seen in trauma patient. Furthermore, a better understanding of the factors that may affect measurements of both tHb and SpHb may decrease inter-measurement variability and further improve the previously published performance.

### 1.2 Study Devices

Masimo pulse CO-Oximeter: Radical-7 is an FDA-cleared pulse CO-Oximeter handheld used for noninvasive and continuous monitoring of several physiological parameters including total hemoglobin concentration. It consists of a portable handheld device and a docking station for charging and transferring data. The docking station used in this study has been upgraded to allow transfer of high resolution wavelength data through a serial cable that is connected to a laptop.

---

# **Evaluation of Non-Invasive Hemoglobin in Trauma Patients**

**HOLC0001 version 2**

---

Masimo Rainbow sensors: a finger probe that consists of a series of light emitting diodes (LEDs) and photodetectors. First, light is emitted through a capillary bed; then, the sensors detect the transmitted light. The signals from the sensor are processed and used to quantify hemoglobin levels. Masimo Rainbow sensors for the measurement of hemoglobin are FDA-cleared for use on adults.

Laptop [REDACTED]

## **1.3 Risk/Benefits**

There will be no direct benefits to the enrolled patients. Future benefits to patients might include a reduction in blood draws and possibly optimized fluid management to the ability to trend moment-by-moment hemoglobin levels in trauma patients. No compensation will be paid to the participants or their families.

The risk from the device is minimal since it is non-invasive and uses wavelengths in the red and near infrared range like a conventional pulse oximeter used in routine clinical practice for over 15 years but can include skin irritation and thermal skin burn from the optical sensors.

## **2 STUDY HYPOTHESIS**

SpHb can be used to identify bleeding patients sooner than standard of care by identifying critical drops between laboratory samples.

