#### **7.2 Study Duration**

The Masimo Radical-7 will remain on the subject for up to the first 24 hours following ED admission or discharge from the ICU/IMU (whichever comes first). Direct subject observation will continue until 1) subject has arrived to the ICU/IMU following ED admission, 2) the subject expires or 3) 24 hours following ED admission or discharge from the ICU/IMU (whichever occurs first). Once direct observation is complete, the research team will continue to monitor the subject admitted to ICU (and had first a.m. lab draw completed) throughout the hospitalization to assess for additional procedures and complications incurred. For subjects who are not admitted to ICU/IMU and do not have a second sample drawn, additional data will be obtained through the trauma registry.

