#### **7.3 Sample Collection**

Blood samples will be collected at time of ED admission and first a.m. lab draw in ICU. The blood samples will be based on clinical need and sent to at least two reference devices: the standard of care reference device for patient, hospital laboratory devices located at MHH, and a cyanomethemoglobin (HiCN) analyzer and a hematology analyzer located at a Masimo facility. For those subjects who have laboratory tests ordered at time of ICU admission, a third sample will be collected and sent to the CeTIR research lab for preparation for the cyanomethemoglobin analyzer at a Masimo facility. The collection of the HiCN and hematology analyzer samples must follow standard laboratory practices for handling of blood products as detailed in the manual of operations with at least 1 mL of blood being collected in an EDTA tube. Each sample will have a unique identifier with the identification key revealed by the site only after the sample has been processed by the Masimo analyzer. The exact time of sampling will be documented for retrospective analysis along with type (venous or arterial) and site of blood sampling, location of patient, time since presentation, and specific hospital laboratory analyzer used.

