#### **7.5 Data Analysis**

This trial will provide baseline data on the performance of SpHb in a population with expected rapid changes in tHb levels. The primary metric to be measured is SpHb's ability to detect critical drops in a trauma population and present the data in a categorical table; statistical significance will be calculated with chi-squared analysis.

The secondary metrics that will be calculated include:

- 1- “Trend capability,” which will be determined by calculating the regression equation and coefficient of determination of a linear mixed effect regression model. The relative differences between data points will be represented graphically with polar plots [Critchley] and 4 quadrant plots.
- 2- Performance of different devices compared to HiCN values (the gold-standard for measuring hemoglobin concentration in blood), including the variability caused by standard of care laboratory devices.
- 3- Absolute accuracy calculation, which will be done by mean test method error with standard deviation, average root mean squared and graphically through Bland-Altman plots [Bland].

Analysis will be performed on the pooled data set as well as separate analyses on all data with high or low signal confidence respectively.

A total of 150 subjects with at least 2 blood samples will be included in the analysis. As a critical drop would require at least two laboratory data points for reference, the study will be powered in order to be 90% confident of achieving that target knowing that 47% of patients recruited in the previous study had at least two paired data points and that it is expected that 20% of patients will be excluded after enrollment (no data points).

An interim analysis will be performed after 50 cases with at least 2 blood samples per case have been completed. This will allow determination of the final sample size in order to obtain an appropriate definition of critical drop detection. The final sample size may be adjusted as a result of this analysis.

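### Section 2 claims that SpHb finds bleeding earlier than standard care, but no metric in section 7.5 has time as an outcome

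*Combined protocol and SAP*

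**What the plan says.** Section 2 is a single sentence: "SpHb can be used to identify bleeding patients sooner than standard of care by identifying critical drops between laboratory samples". It names a comparator (standard of care) and a mechanism (drops falling between laboratory samples).

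Section 7.5 gives the primary metric as the ability of SpHb to "detect critical drops in a trauma population and present the data in a categorical table", tested by chi-squared. The three secondary metrics are trend capability (mixed-model regression, polar and four-quadrant plots), performance of the devices against cyanomethemoglobin, and absolute accuracy (mean error with SD, root mean square, Bland-Altman). On what makes a critical drop, the section offers only the clause "As a critical drop would require at least two laboratory data points for reference". It gives no drop size, time window or SpHb rule. Of the interim analysis after 50 cases it says: "This will allow determination of the final sample size in order to obtain an appropriate definition of critical drop detection".

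Some timing data are collected:

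- Section 7.3 places draws at ED admission and at the first morning ICU draw. It adds "The blood samples will be based on clinical need" and "For those subjects who have laboratory tests ordered at time of ICU admission, a third sample will be collected". It also states "The exact time of sampling will be documented for retrospective analysis".
- Section 7.1 has the monitor time-synchronized. Section 7.2 says that it "will remain on the subject for up to the first 24 hours following ED admission", or until ICU/IMU discharge if that comes first.
- Section 7.4 names timing for blood products. Neither the time a laboratory result came back nor the time bleeding was clinically recognised is listed.

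**The concern.** The hypothesis is about earliness, and the analysis is about agreement. If the chi-squared test is significant, it will be natural to report section 2 as supported, although the plan contains no quantity that measures how early SpHb was, or whether it was early at all. Section 1.1 argues for the device from a laboratory delay of up to one hour, but no analysis sets that delay against an SpHb time.

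The link between the table and the hypothesis rests on what counts as detection. Section 7.5 ties that definition to an interim look at 50 of the planned 150 cases, one third of the data. If it is chosen after those cases are seen, the bearing of the primary result on section 2 is settled after the fact.

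**Working it through.** The plan gives no figure for earliness, so there is none to reproduce. Its sample-size reasoning in section 7.5 concerns only the number of subjects with two paired values.

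**1. Does any metric have time as an outcome?**

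| Metric in section 7.5 | What it measures | Time as outcome? |
|---|---|---|
| Primary: drop table, chi-squared | association of SpHb drop with laboratory drop | no |
| Secondary 1: trend | direction and size of change | no |
| Secondary 2: devices against cyanomethemoglobin | agreement with reference | no |
| Secondary 3: absolute accuracy | error, SD, root mean square | no |

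The count is 0 of 4.

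**2. Could the drop table carry time order?** Two readings of detection fit the text.

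- *Comparison at the paired values.* SpHb change is taken at the laboratory sampling times. SpHb then gains nothing over the draw itself, only over the laboratory turnaround.
- *SpHb drop before the later draw.* A positive cell then implies that SpHb came first, as a yes or no.

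The documents do not say which applies. Under either, a given table is unchanged whether the lead in its positive cells is minutes or hours, so it cannot yield the size of the lead.

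**3. What could a lead be measured against?** Draw time is recorded and the monitor is synchronized, so lead over the draw can be computed. Lead over result return or over clinical recognition of bleeding needs times that are not listed.

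**4. Why median lead is a weak summary.** Lead within an interval cannot exceed the interval. Assume a 05:00 morning draw and no draw in between. Arrival at 23:00, 17:00 or 07:00 gives intervals of 6, 12 or 22 h. The longest possible lead therefore varies more than threefold with arrival time alone.

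**5. Why no-drop intervals are needed beside it.** Suppose SpHb drops unrelated to hemoglobin occur at an assumed rate r per hour. The chance of at least one in 12 h is 1 - exp(-12r), which is 0.213, 0.451 and 0.699 for r = 0.02, 0.05 and 0.10. At 0.05 per hour, about 45% of intervals would show an apparently early detection by chance.

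**6. Precision of the proposed measure.** Assume that 10% or 30% of 150 subjects have a laboratory drop (15 or 45), that 80% of these are detected before the draw (12 or 36), and one interval per subject.

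- Wilson 95% CI: 12/15 gives 0.548 to 0.930; 36/45 gives 0.662 to 0.891.
- With about 45% of the no-drop intervals positive, the Newcombe 95% CI for the difference is: 12/15 against 61/135, 0.348 (0.083 to 0.501); 36/45 against 47/105, 0.352 (0.184 to 0.482).

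**The case against.** The best defence is that section 2 supplies its own mechanism. A drop seen between two laboratory samples precedes the second by construction, so a metric of critical-drop detection does address the hypothesis. This stands in part: with the right definition the table would carry time order. But that definition is absent, the talk of paired data points fits the other reading equally well, and the size of the lead is missing either way.

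A second defence is that timing data exist. They do, and that makes a fix cheap, but recording times is not a plan to analyse them. A reader might infer that the comparator has no recorded time at all. That goes too far: draw time is recorded, and the list in section 7.4 is not worded as exhaustive, so result times might be recoverable from the medical record.

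A third is that the study is non-interventional and meant to give baseline data. That is a good reason to prefer rewording section 2. It is not a reason to keep a claim about time that nothing tests.

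It is also fair to object that a lead-time analysis has its own hazard, because lead largely follows draw spacing (step 4). This stands, and it is why median lead should be descriptive only.

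**Conclusion.** The concern holds in this form: the hypothesis asserts earliness, 0 of the 4 metrics in section 7.5 measure it, and the primary table could speak to time order only under a definition not yet given. This rests on reading sections 2 and 7.5 and on no assumed number. The rates in steps 4 to 6 are assumptions and serve only to size the remedy.

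Three stronger readings are not supported:

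- *That the study can say nothing about time order.* It could, if detection required SpHb to come before the draw.
- *That the choice of definition decides whether the primary test is significant.* The documents give no counts. A stricter rule would lower SpHb detections in subjects with and without a laboratory drop, so an example that tightens it in one group alone proves nothing.
- *That no lead-time analysis exists anywhere in the plan.* The text between sections 3 and 5 and the manual of operations were not available.

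The data remain usable, so this is a matter to correct before the interim look rather than a fatal flaw.

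**What to change.** Choose one of two routes.

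**(a) Reword section 2.** State the hypothesis as detection of drops seen at paired laboratory draws, and remove the claim of an advantage in time over standard care. This is the simplest repair. It costs one sentence and gives up the earliness claim.

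**(b) Keep a claim about time and test it.** Before the 50-case interim look, add to section 7.5:

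1. A definition: detection requires a sustained SpHb drop of a prespecified size before the laboratory draw that shows the drop. Define what sustained means and the SpHb baseline. Section 7.1 places the sensor after the secondary survey, so the ED draw may come first.
2. A secondary analysis: the share of all laboratory drops detected before the draw, with a 95% CI. Drops that SpHb misses count as not detected early.
3. Beside it, the share of no-drop intervals of similar length that show an SpHb drop.
4. Median lead as description only, labelled as dependent on draw spacing and conditional on detection.
5. A conclusion limited to lead over the laboratory draw. Lead over clinical recognition of bleeding should not be claimed.

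Route (b) needs specification and programming but no extra subjects or draws. Its price is modest precision, as in step 6, and a narrower claim.

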## **3 STUDY DESIGN**

This is a prospective, non-blinded, non-randomized, non-interventional study of the Masimo pulse oximeter and sensors in a trauma setting.

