### **7 STUDY PROCEDURES**

#### **7.1 Study Procedures**

Data collection will begin immediately within the first few minutes after admission to the emergency department. The SpHb butterfly sensor will be placed according to instructions in the manual of operations, [REDACTED] and connected to a time-synchronized Masimo Radical-7. Sensor placement will occur after the patient's position has been stabilized and after the secondary survey has been completed. The sensor will be placed, in order of preference, on the ring or middle finger of the non-dominant hand, the ring or middle finger of the dominant hand, the index finger of non-dominant hand, the index finger of the dominant hand. The sensor will not be placed on the thumb or the small finger, nor shall it be placed on any other location on the patient's body. The measurement site must be clean, have no deformity with any part of the finger including nail bed and have no trauma on the arm or forearm proximal to the site of sensor placement.

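### SpHb is not stated to be masked and reference draws follow clinical need, so the device may influence both its own reference test and the standard of care it is compared with

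*Combined protocol and SAP*

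**What the plan says.** Section 3 calls the trial a "prospective, non-blinded, non-randomized, non-interventional study of the Masimo pulse oximeter and sensors in a trauma setting". Section 7.2 sets the wearing time: "The Masimo Radical-7 will remain on the subject for up to the first 24 hours following ED admission", or until ICU/IMU discharge if that comes sooner.

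Section 7.3 names two sampling times: "Blood samples will be collected at time of ED admission and first a.m. lab draw in ICU". Its next sentence qualifies them: "The blood samples will be based on clinical need". A further sample is conditional: "For those subjects who have laboratory tests ordered at time of ICU admission, a third sample will be collected". For each sample the plan records the time, whether it was venous or arterial, the site, the patient's location, the time since arrival and the analyzer used. The reason for the draw is not on that list. Sample identity is coded until the sponsor's analyzer has processed the sample.

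Section 7.1 fixes when SpHb readings can begin: "Sensor placement will occur after the patient's position has been stabilized and after the secondary survey has been completed".

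The hypothesis in section 2 is that "SpHb can be used to identify bleeding patients sooner than standard of care". Section 7.5 makes detection of critical drops the primary metric, shown in a categorical table with a chi-squared test, and requires two or more blood samples per analysed subject.

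**The concern.** SpHb is the index test and the laboratory value is the reference. If treating staff can see SpHb, a falling value may prompt a draw and a reassuring one may postpone it. Patients would then reach the primary table partly because of the result under evaluation.

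Two things are at stake. The first is the proportions in the critical-drop table, which depend on which patients, and which intervals, have a laboratory pair. The second is the hypothesis itself: if SpHb helps decide when the laboratory sample is taken, standard of care is no longer an independent comparator. The non-interventional label would also lack any stated protection.

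**Working it through.** **Is the pathway open?** Setting the sections side by side:

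- Visibility: section 3 says non-blinded, and no available section masks the display or bars acting on SpHb.
- Overlap in time: up to 24 hours of monitoring (section 7.2) spans the ICU-admission draw and may span the first morning draw.
- Discretion: sampling follows clinical need, and the ICU-admission sample needs an order (section 7.3).
- Limit: the ED-admission draw may come before the sensor is on (section 7.1), so the exposure lies in later draws.
- Safeguard: coding of sample identity protects the reading of the assay, not the decision to draw.

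Section 7.5 reports that 47% of patients in the previous study had two or more paired points. Lack of verification may therefore be common, although the plan does not say why pairs were missing.

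**What could it do to the table?** The plan gives no sensitivity, specificity, drop prevalence or verification rate, so there is no plan figure to reproduce and every input below is assumed. Let Se and Sp be the true values, v1 and v0 the probabilities that SpHb-positive and SpHb-negative patients have the needed laboratory pair, and R = v1/v0.

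- Apparent Se = Se·v1 / [Se·v1 + (1 − Se)·v0]
- Apparent Sp = Sp·v0 / [Sp·v0 + (1 − Sp)·v1]

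Prevalence cancels from both, and only R matters.

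With Se 0.50, Sp 0.90, v1 0.90 and v0 0.60 (R = 1.5):

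- Apparent Se = 0.45/(0.45 + 0.30) = 0.60
- Apparent Sp = 0.54/(0.54 + 0.09) = 0.857

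With v0 0.40 (R = 2.25):

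- Apparent Se = 0.45/(0.45 + 0.20) = 0.692
- Apparent Sp = 0.36/(0.36 + 0.09) = 0.80

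A second assumed starting point, Se 0.70 and Sp 0.80, shows the range:

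| R | Apparent Se | Apparent Sp |
|---|---|---|
| 0.8 | 0.651 | 0.833 |
| 1 | 0.700 | 0.800 |
| 1.25 | 0.745 | 0.762 |
| 1.5 | 0.778 | 0.727 |
| 2 | 0.824 | 0.667 |
| 3 | 0.875 | 0.571 |

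**What happens to the association?** The odds ratio is [Se/(1 − Se)]·[Sp/(1 − Sp)], and R cancels from it. In the first example the true value is 1 × 9 = 9. The two apparent values are 1.5 × 6 = 9 and 2.25 × 4 = 9. Verification that depends only on the SpHb result therefore cannot create an association where none exists.

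**Can the effect run the other way?** Suppose visible SpHb also prompts treatment that removes the drop before the draw in a share t of true positives. Then apparent Se = Se·R·(1 − t) / [Se·R·(1 − t) + 1 − Se]. With Se 0.70 and t = 0.30:

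- R = 1: 0.49/0.79 = 0.62
- R = 1.5: 0.735/1.035 = 0.71
- R = 2: 0.98/1.28 = 0.77

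Without the treatment effect these would be 0.70, 0.78 and 0.82.

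**Lead time.** SpHb's lead is the time of the laboratory finding minus the time of the SpHb signal. A draw prompted by SpHb brings the laboratory time forward, so the measured lead tends to shrink.

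**The case against.** The strongest reply is that visibility to clinicians is inferred. Non-blinded does not say that treating staff read or act on SpHb. Section 3 also says non-interventional, and section 1.3 promises no direct benefit. The text between sections 3 and 5, the manual of operations and the redacted parts of sections 7.1 and 7.4 could not be checked, and masking may be described there. This stands as a limit on certainty. If masking exists, section 3 should say so.

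Next, the two named sampling times could supply the required pair without any trigger, and the missing second samples mentioned in section 7.2 concern patients not admitted to the ICU/IMU, which is a matter of disposition. This narrows the exposure but does not close it: section 7.3 makes sampling need-based straight after naming the times, and section 7.5 does not say which draws enter the primary table.

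Third, section 7.5 names a categorical table and a chi-squared test, not sensitivity, and the odds ratio survives unequal verification. That is correct, and it removes any charge that this mechanism alone manufactures significance. The detection proportions a reader would take from the table remain exposed.

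A reader might infer that the design inflates sensitivity in the device's favour. The documents do not support that. Inflation needs SpHb-positive patients to be verified more often, it comes with lower specificity, and early treatment can offset it. Nor is this differential verification, which would mean different reference standards for positives and negatives; the issue is whether verification happens at all.

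**Conclusion.** The point holds as an open pathway, not as a demonstrated bias. Nothing in the available text prevents SpHb from affecting whether and when later reference samples are taken, or allows that influence to be measured afterwards.

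The possible size is material. In the assumed examples, R between 1.5 and 2.25 adds about 8 to 19 percentage points to apparent sensitivity and takes about 4 to 13 points off specificity. These figures rest wholly on assumed accuracy and verification ratios. The direction is not fixed, because treatment before the draw can pull apparent sensitivity down.

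The standard-of-care comparison is contaminated if SpHb is visible and acted on. A reader might take this as favouring the hypothesis in section 2, but draws brought forward would tend to work against it. The sponsor therefore has its own reason to close the pathway. The change is worth making because it is cheap and fits the non-interventional, no-direct-benefit design.

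**What to change.** In section 3, state that the SpHb parameter on the study Radical-7 is hidden from the treating team while recording continues, and bring the blinding description into line with that.

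Where masking is not possible, add two items to the per-sample record in section 7.3: the reason the draw was ordered, and whether SpHb was visible beforehand. In section 7.5, add a sensitivity analysis that excludes draws ordered after SpHb was seen.

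Restricting the primary table to the two named draws is not advised. It would leave many subjects with a single interval, although the hypothesis concerns drops between laboratory samples, and the first draw may have no SpHb baseline.

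The cost is a short amendment, staff effort to configure or cover the display, and one or two CRF items. Reasons for draws that are not captured at the time may be impossible to recover later.
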